#### 4.3 Justification for Dose

The selected dose for this trial is 10 mg glepaglutide once-weekly for 52 weeks. The selected dose is considered supported with respect to both safety and efficacy, as described below.

# **4.3.1** Safety

The safety of the proposed dose is supported by the outcome of the completed clinical trials, which showed that single SC administrations up to 20 mg and total weekly doses of 10 mg, 70 mg or 140 mg all appeared well tolerated. No safety issues were raised in these trials, which included maximum plasma concentration ( $C_{max}$ ) and overall exposure levels well above those proposed for this phase 3b trial. From a safety perspective, once-weekly SC injections of 10 mg glepaglutide is therefore considered to be an appropriate dose level for testing in phase 3b.

### 4.3.2 Efficacy

Using the data from the glepaglutide PK trial ZP1848-16182, the average steady-state plasma concentration in the dosing interval ( $C_{avg}$ ) and the associated 90% prediction interval can be calculated for 10 mg glepaglutide dosed once-weekly (based on observed data). These average plasma concentrations and associated 90% prediction intervals are shown superimposed on the exposure-response curve established for the phase 2 primary endpoint in supporting that once-weekly dosing of 10 mg glepaglutide results in glepaglutide concentrations within the therapeutically effective dose range (see Figure 2).

[figure not shown]

Figure 2 Exposure-Response Curve

Investigating the assumption that a minimum plasma concentration is needed to drive efficacy, the analysis predicts that a once-weekly dosing regimen of 10 mg glepaglutide would result in plasma concentrations within the therapeutically effective range for several days after dosing, but possibly falling below the therapeutically effective level during the latter phase of each weekly dosing interval. This dosing regimen is expected to result in a therapeutically relevant overall effect based on the current knowledge of biological activities related to GLP-2 receptor activation.

#### 4.4 End of Trial Definition

A patient is considered to have completed the trial when he or she has completed trial product treatment for 52 weeks and completed both metabolic balance study periods (at Visit 1 and 9) as well as the final safety assessments at Visit 12 and completed the follow-up visit (week 56).

The end of the trial is defined as the date of the last visit (follow-up visit) of the last patient in the trial.

#### 5 TRIAL POPULATION

The patient population selected for this trial must have SBS with intestinal insufficiency or intestinal failure. Since patients with SBS-II compensate with an increased oral intake of fluid and food, they can have as large fecal output as patients with SBS-IF. Thus, fecal output is important to assess in both patients with SBS-II and SBS-IF.

The impact of SBS on quality of life seems to depend on the degree of malabsorption and thus the need for PS: the higher the need for PS, the greater negative impact of SBS on quality of life. Hence, for the population of patients with SBS-IF there exists an unmet need for medical treatment to reduce the burden of malabsorption and PS.

Prospective approval of protocol deviations to recruitment and enrollment criteria, also known as protocol waivers or exemptions, is not permitted.

#### 5.1 Inclusion Criteria

Patients are eligible to be included in the trial only if all of the following criteria apply:

- 1. Informed consent obtained before any trial-related activities. Trial-related activities are any procedures that are carried out as part of the trial, including activities to determine suitability for the trial.
- 2. Age  $\geq 18$  years and  $\leq 90$  years at screening.
- 3. Willing to comply with trial procedures, including 2 in-house visits with urine and fecal output collection.
- 4. Stable condition of SBS either with intestinal failure (IF) or intestinal insufficiency. For patients with SBS-IF a stable condition is defined as < 25% change in PS volume or energy content for 4 weeks prior to screening.
- 5. Stable body weight (<5% change in weight in the 3 months prior to screening).
- 6. Wet weight of fecal excretion ≥1,500 g/day demonstrated during a hospital stay prior to screening\*.

\*If inclusion criteria #6 cannot be met, a visit may be scheduled where fecal output collected at home by the patient or during a hospital stay can be assessed. If the wet weight of fecal excretion ≥1,500 g/day can be demonstrated, the criterion #6 is met.

### 5.2 Exclusion Criteria

Patients are excluded from the trial if any of the following criteria apply:

#### General

- 1. Current, or within 30 days prior to screening, participation in another interventional clinical trial that includes administration of an active compound.
- 2. Mental incapacity or language barriers which preclude adequate understanding or cooperation, or unwillingness to comply with trial requirements.
- 3. Previous participation in this trial. Participation is defined as having received trial product.
- 4. Females of childbearing potential, who are pregnant, breast-feeding, intend to become pregnant or are not using highly effective contraceptive methods. Male patients with female partners, who intend to become pregnant.

### Medical history and concomitant diseases

- 5. More than 2 SBS-related or PS-related hospitalizations (e.g., catheter-related bacteremia/sepsis, bowel obstruction, severe water-electrolytes disturbances, etc.) within 6 months prior to screening.
- 6. Poorly controlled inflammatory bowel disease (IBD) that is moderately or severely active or fistula interfering with measurements or examinations required in the trial.
- 7. Current bowel obstruction.
- 8. Known radiation enteritis or significant villous atrophy, e.g., due to active celiac disease.
- 9. Cardiac disease defined as: decompensated heart failure (New York Heart Association [NYHA] Class III-IV), unstable angina pectoris, and/or myocardial infarction within the last 6 months prior to screening.
- 10. Clinically significant abnormal electrocardiogram (ECG) as judged by the Investigator.
- 11. Human immunodeficiency virus (HIV) positive, acute liver disease including positive results for Hepatitis B antigens (HBsAg) and Hepatitis C (HCV), or unstable chronic liver disease.
- 12. Any history of colon cancer. History of any other cancers (except margin-free resected cutaneous basal or squamous cell carcinoma or adequately treated in situ cervical cancer) unless disease-free state for at least 5 years.
- 13. Hepatic impairment defined as:
  - a. Total bilirubin  $\geq 2 \times$  the upper limit of normal (ULN), or
  - b. Aspartate aminotransferase (AST)  $\geq$  5 × ULN, or
  - c. Alanine aminotransferase (ALT)  $\geq$  5× ULN
- 14. Use of GLP-1, GLP-2, human growth hormone (HGH), somatostatin, or analogs thereof, within 3 months prior to screening.
- 15. Known or suspected hypersensitivity to glepaglutide, its components or related products.
- 16. Use of dipeptidyl peptidase (DPP)-4 inhibitors within 3 months prior to screening.
- 17. Surgical resection of gut tissue within 6 months prior to screening.
- 18. Systemic immunosuppressive therapy for treatment of the gastrointestinal tract that has been introduced or has been unstable within 3 months prior to screening.
- 19. Unstable biological therapy (e.g. anti-TNF-α, natalizumab, etc.) within 6 months prior to screening, including significant changes in doses or switch of drug.

# 5.3 Lifestyle Consideration

### 5.3.1 Dietary Restrictions

The patients must follow an individual 'drinking menu' (which will be set during the screening phase) on the days of the metabolic balance study during hospital admissions (Visit 1 and Visit 9) as well as on the days of 48-hour urine collection at home prior to each visit up to and including Visit 9. The drinking menu starts on the same day as the 48-hour pre-visit urine collection, and lasts for a total of 48 hours (see Section 8.2.2).

Fasting is required for blood sampling for citrulline, cholesterol and triglycerides (see Section 8.2.13). Fasting is defined as no intake of food or drinks, except water, for at least 10 hours (±1 hour) (since app. 22:00h) the day before the blood sampling. PS administration is allowed.

For other laboratory tests, fasting is optional.

# 5.3.2 Smoking

Smoking is not permitted the last 2 hours prior to blood sampling for citrulline (see Section 8.2.13).

#### 5.4 Screen Failures

Screen failures are defined as participants who consent to participate in the clinical trial but are not subsequently assigned to trial intervention. A minimal set of screen failure information is required to ensure transparent reporting of screen failure participants to meet the Consolidated Standards of Reporting Trials (CONSORT) publishing requirements and to respond to queries from regulatory authorities. Minimal information includes demography, screen failure reason(s), eligibility criteria, and any SAE. A screen failure rate of 10% is expected.

Individuals who do not meet the criteria for participation in this trial (screen failure) may be rescreened. Rescreened participants should be assigned a new participant number for every screening/rescreening event.

# 5.5 Dosing Criteria

The first dose of trial product must only be administered after the baseline metabolic balance study as well as all other baseline assessments are completed at Visit 1.

To be eligible for dosing, all inclusion criteria must be met and none of the exclusion criteria.

Re-sampling is not allowed if the patient has failed any of dosing criteria related to laboratory parameters. However, in case of technical issues (e.g. hemolysed or lost), re-sampling is allowed for the affected parameters.

#### 6 TREATMENTS

### **6.1** Treatment Administered

The trial product for the trial is described in Table 5.

**Table 5** Trial Product

| Trial Product Name        | Glepaglutide 20 mg/mL   |
|---------------------------|---|
| Dose Formulation          | Solution for injection  |
| Unit Dose Strength | 10 mg/0.5mL   |
| Dosage Level              | 10 mg once-weekly   |
| Route of Administration   | SC injection  |
| Sourcing                  | By Sponsor  |
| Packaging and Labeling    | Trial product will be provided in single-use autoinjectors containing 0.5 mL of 20 mg/mL glepaglutide (clear, essentially colorless solution). Each autoinjector and box will be labeled in accordance with Annex 13, country and trial requirements. |
| Storage                   | Store in refrigerator between 2°C – 8°C.  Protect from light  |

Additional details regarding the trial product can be found in the trial materials manual. Each dispensing unit/pen is uniquely numbered with a dispensing unit number.

# **6.1.1** Trial product administration

Patients must choose their preferred injection site area; either on their abdomen or their thigh(s). Unless otherwise agreed with the Investigator, patients must use this selected injection site area during the entire trial. The specific injection site must be rotated for each weekly injection such that the injections are administered at least 5 cm away from the last injection administered, and still within the same injection site area, i.e., abdomen or thigh. It is acceptable to inject in one thigh or both thighs during the treatment period. Only patients eligible for treatment must use trial product and only delegated site staff must dispense or administer trial product. No trial product may be dispensed to any person not enrolled in the trial.

# 6.2 Handling/Storage/Accountability

### **6.2.1** Handling and Storage

The Sponsor will provide trial product for each patient for the duration of his/her participation in the trial. The Investigator, or designee will dispense trial product at each dispensing visit. A sufficient quantity of trial product will be dispensed to assure that the patient has sufficient trial product supply to last at least until the next scheduled drug dispensing visit. The Investigator, or designee must ensure that no patient uses expired trial product at any time.

Patients will be familiarized with the handling and use of the autoinjector prior to the first administration of trial product, and as needed at the site. The Investigator must document that Instructions for use are given to the patient verbally, and in writing at all dispensing visits (as specified in the flowchart).

The Investigator must maintain an accurate record of the shipment and dispensing of trial product.

The Investigator or designee must instruct the patient in what to return at next visit to the clinic.

All returned (used and unused), expired or damaged trial products (for technical complaint samples, see section 8.4.8) must be stored separately from non-allocated trial products and can be done at room temperature. No temperature monitoring is required.

In case the Investigator, the site staff, or the monitor suspect that the trial drug is defective or potentially defective, the Sponsor should be contacted immediately.

### 6.2.2 Accountability

The Investigator must ensure that a designated person receives trial product deliveries from the Sponsor or designee and that all such deliveries are:

- Recorded
- Handled and stored safely and properly
- Returned to sponsor or designee, as required

The Investigator or designee must keep drug inventory and accountability logs of which a copy must be given to the Sponsor at the end of the trial. An accurate record of the date and amount of trial product dispensed to and returned from each patient must be available for inspection at any time. The inventory log will include details of the trial product received and dispensed to the patient. All used and unused autoinjectors and the dispensing cartons must be kept and returned to the monitor who will perform reconciliation of delivery records and accountability logs. Discrepancies between the amount of trial drug received, dispensed and returned will be verified.

Patients should be instructed to bring all their trial product including the dispensing cartons to each scheduled trial visit. Investigator or delegated staff must perform drug accountability with the patient at every visit to the clinic. Returned trial product (used or unused autoinjectors and the dispensing cartons) must be stored separately from non-allocated trial product.

The Investigator must not destroy any used or unused trial product supplies. At the conclusion of the trial (or by agreement with Sponsor during the trial if storage capacity at site is limited) the Investigator will return all used and unused trial drug and the dispensing cartons to the Sponsor.

### 6.3 Measures to Minimize Bias: Randomization and Blinding

This is a single-arm, fixed dose trial and all patients will receive the same treatment. No randomization and blinding will be performed.

The primary and key secondary endpoints are addressing the absorptive capacity of the intestines and are thus objective. They are derived from laboratory measurements of the input and output during the balance studies. To minimize bias on the wet weight absorption, fluid intake during the balance study is restricted to a drinking menu.

Adjustment of PS for patients with SBS-IF, will be done according to an algorithm that takes the urine output at baseline and during the 48h periods along with the current PS into account. This will limit the bias of the open-label design.

# **6.4** Treatment Compliance

# **6.4.1 Drug Treatment Compliance**

Throughout the trial, the Investigator will remind the patients to follow the trial procedures and requirements to encourage patient compliance.

During the trial, patients will mainly self-administer trial product at home. The first dose will be administered at the trial site.

Patients are requested to enter details regarding trial product administration (including date and time of the day as well as dispensing unit number) and injection site area used (i.e., abdomen, thigh) in the diary and transcribed to the eCRF.

Patients are to record PS use (including bag name, volume and infusion date) in the diary on an ongoing basis, and must be checked and transcribed into the eCRF at every visit by the Investigator.

When patients self-administer trial product at home, compliance with trial product administration will be assessed and documented in source documents at each visit where information is available. If any suspicion of non-compliance arises, the site must start a dialogue with the patient, re-emphasizing the importance of compliance, uncover barriers to compliance, and retrain the patient, if needed. This dialogue must be documented. Compliance will be assessed by cross-checking the following sources and comparing these to the expected use:

- Drug accountability information; visual inspection of returned autoinjectors
- Review of patient diaries

The Investigator must ensure that patients who temporarily discontinue treatment with trial product due to safety concerns, e.g. admission to hospital, are resuming treatment safely to avoid dehydration.

### **Missed Doses of Trial Drug**

Patients should not omit planned doses. Patients who miss a scheduled dose of trial product should be instructed to administer the missed dose as soon as they become aware of the mistake; however, 2 doses should not be administered the same day.

# 6.4.2 Compliance with 48-hour Drinking Menu

Compliance to the drinking menu in association with the at-home 48-hour urine collection prior to each visit (up to and including Visit 9) will be assessed by review of patient diaries, where the patients will record their fluid intake (see Section 8.2.2).

# 6.5 Concomitant Therapy

Medications commonly used to treat SBS symptoms including anti-diarrhea agents are allowed during trial participation; however, changes (start, stop, new brands, or dose changes) should be kept to a minimum and the Medical Monitor be informed on the indication for the change via reporting in the eCRF.

Any medication or vaccine (including over-the-counter or prescription medicines, vitamins, and/or herbal supplements) other than the trial product that the patient has taken within 7 days

prior to and including the screening visit, or receives during the trial must be recorded along with:

- Trade name or generic name
- Indication
- Dates of administration including start and stop dates
- Dose (total daily), unit and route of administration

Changes in concomitant medication must be recorded at each visit. If a change is due to an AE, then this must be reported according to Section 8.4.

The Sponsor should be contacted if there are any questions regarding concomitant or prior therapy.

#### 6.6 Prohibited Medication

GLP-1 analogs, GLP-2 analogs (teduglutide), HGH, DPP-4 inhibitors, and somatostatins are not allowed to be used by patients during the course of the trial.

Medications commonly used to treat SBS symptoms including anti-diarrhea agents are allowed during trial participation; however, changes (start, stop, new brands, or dose changes) should be kept to a minimum and the reason for the change should be recorded in in eCRF. Any changes to concomitant medications must be documented in the eCRF.

#### 6.7 Dose Modification

Not applicable.

### 6.8 Treatment After the End of the Trial

When discontinuing trial product (Visit 12), the patient should be treated according to the standard of care at the discretion of the Investigator or treating physician.

### 7 DISCONTINUATION OF TRIAL PRODUCT AND PATIENT WITHDRAWAL

### 7.1 Discontinuation of Trial Treatment

Treatment of a patient may be discontinued at any time during the trial at the discretion of the Investigator for safety reasons. However, the patient can still continue, and should be encouraged to stay in the trial if assessed safe according to the Investigator.

Efforts must be made so that patients continue to attend and complete all scheduled visit procedures to the extent possible. Patients should stay in the trial regardless of compliance with trial drug, assessments, or visit schedule. The Investigators should make a special effort to ensure that all patients complete the assessment for the primary and key secondary endpoints.

Patients must be educated about the continued scientific importance of their data, even if they discontinue trial product.

A patient must be discontinued from trial treatment if:

- 1. Any safety concerns or AEs that in the opinion of the Investigator might place the patient at unacceptable risk, including any deterioration of a patient's health state, especially in terms of the frequency and volume of total PS.
- 2. Any malignancy.
- 3. Increased liver values, defined as:
  - a. ALT or AST >3 times baseline value lasting more than 2 weeks\*, or
  - b. ALT or AST  $>5 \times$  ULN and total bilirubin  $>2 \times$  ULN\*, or
  - c. ALT or AST  $>5 \times$  ULN and international normalized ratio (INR) >1.5\*, or
  - d. ALT or AST  $>5 \times$  ULN with the appearance of fatigue, nausea, vomiting, right upper quadrant pain or tenderness, fever, rash, and/or eosinophilia (>5%)\*
  - \* where no other etiology exists.
- 4. Pregnancy or intention to become pregnant.
- 5. The patient requires treatment with prohibited medications (see Section 6.6).

Patients can be discontinued from trial treatment if:

• A patient was enrolled despite it was later identified that some of the inclusion or exclusion criteria were violated. The Investigator must discuss with the Sponsor's Medical Monitor if it is safe for the patient to continue the trial treatment. If a patient prematurely discontinues trial treatment, the primary reason must be specified in the eCRF. If the patient continues in the trial without trial treatment, the intent should be to follow the patient to the extent possible according to the planned visit schedule and assessments with the purpose of following the safety and efficacy of the patients. Reason for visits not having been performed must be documented.

#### 7.2 Patient Withdrawal from the Trial

A patient may withdraw from the trial at any time at his/her own request (withdrawal of consent). The patient's request to withdraw from the trial must always be respected. A patient may be withdrawn at any time at the discretion of the Investigator for safety reasons.

A patient must be withdrawn if any of the following applies:

- Withdrawal of informed consent
- Safety concerns or AEs that in the opinion of the Investigator might place the patient at unacceptable risk for further participation in this trial or would likely make the patient unable to carry out the full trial
- Sponsor closure of the trial
- Pregnancy or intention of becoming pregnant

IMPORTANT: Efforts must be made to have the patients to attend the Week 52 end of treatment visit (EoT) and the Week 56 follow-up visit (FU) where all general, safety, and laboratory assessments should be performed as detailed in the flowchart (see section 1.2).

Final drug accountability must be performed even if the patient is not able to come to the site.

If the patient withdraws consent for disclosure of future information, the Sponsor may retain and continue to use any data collected before such withdrawal.

If a patient withdraws from the trial, he/she may request destruction of any samples taken and not tested, and the Investigator must document this in the site trial records.

Although a patient is not obliged to give his/her reason(s) for withdrawing, the Investigator must make a reasonable effort to ascertain the reason(s), while fully respecting the patient's rights. Where the reasons are obtained, the primary reason for withdrawal must be specified in the 'end of trial' form in the eCRF.

All data collected from a withdrawn patient prior to withdrawal and during the final visit will be included in the analyses of the trial data. Although a patient is not obliged to give his/her reason(s) for withdrawing consent, the Investigator must make a reasonable effort to ascertain the reason(s), while fully respecting the patient's rights. An end of trial form must be completed and final drug accountability done even when patients are not able to come for a trial visit. Only patients who withdraw their consent will be considered as withdrawn from the trial.

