### 8.4.5 Pregnancy

Pregnancy during the trial should be avoided and the patients must be instructed in highly effective contraception as per local guidelines (see Contraception Guidance in Appendix 4: Contraceptive Guidance and Collection of Pregnancy Information), and to use this throughout the trial through 4 weeks after receiving the last dose of trial product.

Pregnancy information for female patients and female partners of male patients will be collected after the start of trial treatment and until the follow-up visit.

If a pregnancy is reported, the Investigator should inform the Sponsor within 24 hours of learning of the pregnancy and should follow the procedures outlined in Section 10.4 (Appendix 4).

Abnormal pregnancy outcomes (e.g., spontaneous abortion, fetal death, stillbirth, congenital anomalies, ectopic pregnancy) are considered SAEs.

If a patient becomes pregnant during the trial, the patient should be withdrawn from trial (see Section 7.2).

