# 9.2 Sample Size Determination

Sample size is planned based on both, feasibility considerations and statistical considerations. Sample size should be such that there is sufficient power to reject at least the primary null hypothesis (primary endpoint). In the phase 2 trial, ZP1848-15073, after three weeks of treatment, the pooled 1 and 10 mg/day treatment groups displayed a mean (SD) change from baseline in absorption of wet weight fluids of 719 g/day (340 g/day), corresponding to an effect size (mean divided by standard deviation) of 2.11. Calculations based on a one-sample t-test (alpha= 0,05, two-sided) reveal 90% power for a statistically significant test result of the primary null hypothesis, if an effect size of 2.11 can be assumed and 5 patients are analyzed. The effect size is the true population mean of the 24 week change in wet weight absorption divided by its standard deviation.

In the same trial, the change from baseline in the intestinal energy absorption was 391 KJ/day (1374 KJ/day), corresponding to an effect size of 0.28. While achieving statistical significance for the key secondary endpoint in addition to the primary endpoint is aimed for, a sample size providing high power for the key secondary endpoint is not considered feasible, should a similar variability have to be expected for the present study. It seems, however, reasonable to assume that the variability of results for the key secondary endpoint will be lower after 24 weeks compared to after 3 weeks. Should the reduced variability lead to an effect size of around 1.15, then the below table shows that 90% power can be achieved with 10 patients in the analysis, and 80% power can be achieved with 8 patients in the analysis. Even a less extensive reduction in variability can still lead to a reasonable power with 8 to 10 patients in the analysis.

| Number Of Patients | Effect Size | Power (%) |
|---------------------------|-------------|-----------|
| 8                         | 1,156       | 80        |
| 8                         | 1,2         | 82        |
| 8                         | 1,3         | 88        |
| 8                         | 1,342       | 90        |
| 8                         | 1,4         | 92        |
| 10                        | 0,996       | 80        |
| 10                        | 1,0         | 80        |
| 10                        | 1,1         | 87        |
| 10                        | 1 155       | 00        |

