# **Collection of Pregnancy Information**

# Female patients who become pregnant

- The Investigator will collect pregnancy information on any female patient who becomes pregnant while participating in this trial.
- Female patients must be instructed to notify the Investigator immediately if she becomes pregnant or if she suspects she might be pregnant during the trial.
- All initial reports of pregnancy in female patients must be reported to PharmaLex by the trial site personnel within 24 hours of knowledge of the event using the appropriate pregnancy form.
- The initial information will be recorded on the appropriate form and submitted to the Sponsor within 24-hours of learning of a patient's pregnancy.
- The patient will be followed to determine the outcome of the pregnancy. The Investigator will collect follow-up information on the patient and the neonate, and the information will be forwarded to the Sponsor. Follow-up will not be required for longer than 1 month beyond the estimated delivery date. Any termination of pregnancy will be reported, regardless of fetal status (presence or absence of anomalies) or indication for the procedure.
- While pregnancy itself is not considered to be an AE or SAE, any pregnancy complication or elective termination of a pregnancy for medical reasons will be reported as an AE or SAE.
- Abnormal pregnancy outcomes (e.g. spontaneous abortion [occurring at <22 weeks gestational age], stillbirth [occurring at >22 weeks gestational age], fetal death, congenital anomalies, and ectopic pregnancy) are considered SAEs and must be reported using the SAE form.
- Any post-trial pregnancy related SAE considered reasonably related to the trial intervention by the Investigator will be reported to the Sponsor as described in Section 8.4.1. While the Investigator is not obligated to actively seek this information in former trial patients, he or she may learn of an SAE through spontaneous reporting.
- Any female patient who becomes pregnant while participating in the trial will discontinue trial intervention.

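### Protocol 7.2 contradicts itself on who counts as withdrawn, and its exit route has no balance study, so a patient leaving before Week 24 may have no primary value

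*Protocol*

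**What the plan says.** **Protocol 7.1 (stopping treatment).** A patient who stops trial product can stay in the trial if the Investigator considers it safe. The section adds: "Patients should stay in the trial regardless of compliance with trial drug, assessments, or visit schedule". It asks for a special effort to obtain the primary and key secondary assessments from every patient. A patient who stays without treatment is to be followed on the planned schedule as far as possible. Safety concerns or AEs posing an unacceptable risk, and pregnancy or the intention of it, are among the mandatory reasons to stop treatment.

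**Protocol 7.2 (leaving the trial).** Four triggers make withdrawal mandatory: withdrawn consent, safety concerns or AEs, sponsor closure, and pregnancy or the intention of it. The safety item covers unacceptable risk from further participation, and also events that "would likely make the patient unable to carry out the full trial". On visits it says: "Efforts must be made to have the patients to attend the Week 52 end of treatment visit (EoT) and the Week 56 follow-up visit (FU". The section ends: "Only patients who withdraw their consent will be considered as withdrawn from the trial".

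**Other places.**
- Protocol 8.4.5 on pregnancy: "If a patient becomes pregnant during the trial, the patient should be withdrawn from trial". Appendix 4: "Any female patient who becomes pregnant while participating in the trial will discontinue trial intervention".
- Protocol 4.1 and Table 1 place the balance study at Visits 1 and 9 only.
- SAP 2.1.1.1 makes the withdrawal visit an end-of-treatment examination.
- SAP 4.3.1 applies a treatment policy strategy and includes FAS results whatever the duration of dosing. It also states that collection of treatment-phase data ends after withdrawal from the treatment phase.
- Protocol 7.2.1 rules out replacement. Protocol 9.4.1 and SAP 2.2.3 use observed data only.

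**The concern.** The closing sentence of 7.2 cannot be applied together with the list above it. A patient removed for an AE must be withdrawn under the list and is not withdrawn under the closing sentence. The choice decides whether the Week 24 balance study is sought. Under the 7.1 route it is; under the 7.2 exit route the only visits named contain no balance study.

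The primary and key secondary endpoints both need that one Week 24 measurement, in a trial planned for about 10 patients. If the exit route is followed, the missing values would belong to patients who left because of AEs, and an observed-case mean could then be too favourable. Nothing later in the plan repairs this. Lost patients are not replaced, and the SAP specifies no sensitivity analysis for missing data, although Protocol 9.4.1 left room for one. The FAS requires only one dose, so the aim of at least 8 FAS patients in Protocol 9.2 does not secure 8 Week 24 values.

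**Working it through.** **1. The texts side by side.**

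| Situation before Week 24 | 7.1 | 7.2 list | 7.2 closing sentence | Week 24 balance study sought? |
|---|---|---|---|---|
| Consent withdrawn | not covered | withdrawn | withdrawn | no |
| Safety concern or AE | off drug, stays if safe | withdrawn if participation is the risk or the trial cannot be completed | not withdrawn | depends on the text followed |
| Sponsor closure | not covered | withdrawn | not withdrawn | not stated |
| Pregnancy or intention | off drug | withdrawn | not withdrawn | depends on the text followed |

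Three of the four listed triggers conflict with the closing sentence. SAP 4.3.1 adds a second conflict: Week 24 lies inside the 52-week treatment phase, so stopping collection on withdrawal from that phase removes data that the treatment policy strategy is meant to use.

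**2. The plan's own sample size.** Protocol 9.2 states: "Calculations based on a one-sample t-test (alpha= 0,05, two-sided) reveal 90% power" for 5 analysed patients. The input is the phase 2 pooled group, which "displayed a mean (SD) change from baseline in absorption of wet weight fluids of 719 g/day (340 g/day"), so d = 719/340 = 2.11. For a one-sample t-test, power = P(|T| > t(0.975, n−1)), where T is noncentral t with n−1 degrees of freedom and noncentrality d√n.
- n = 4: 79.4%. n = 5: 93.4%. The stated 5 is the smallest n that reaches 90%, so the figure reproduces.

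**3. Effect of losses on power.**

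| Usable Week 24 values | Primary, d = 2.11 | Key secondary, d = 1.15 |
|---|---|---|
| 10 | >99.9% | 89.8% |
| 8 | 99.9% | 79.6% |
| 6 | 98.2% | 61.9% |

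The 1.15 is the effect size that Protocol 9.2 hopes for. The phase 2 value was 391/1374 = 0.28, which gives about 13% power at n = 10 and 11% at n = 8, so there is little to lose in that case.

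**4. Possible bias in the primary mean (scenario).** Assume 10 dosed, one lost before Week 24, the other nine averaging 719 g/day, and the lost patient's change equal to m. The all-patient mean is (9 × 719 + m)/10, and the excess of the observed mean is (719 − m)/10.
- m = 719: excess 0.
- m = 359.5 (half): excess 36 g/day.
- m = 0: all-patient mean 647 g/day, excess 72 g/day, ratio 719/647 = 1.11.

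**5. Does the primary test change in that scenario?** Assume SD 340 among the nine.
- Nine only: t = 719/(340/√9) = 6.3.
- Ten, including the zero: sum of squares = 8 × 340² + 9 × (719 − 647.1)² + 647.1² = 1,390,065. SD = √(1,390,065/9) = 393, and t = 647.1/(393/√10) = 5.2.

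Both give p < 0.001.

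**The case against.** The strongest reply is that the two sections can nest. The 7.2 safety item concerns risk from further participation, 7.1 keeps patients only if that is judged safe, and the 7.2 item on not completing the trial is tied to safety events rather than to poor compliance. On that reading, drug unsafe means stop the drug, and participation unsafe means leave. This largely stands: the triggers overlap and are not the same set of events. But the boundary is left to judgement, and the closing sentence of 7.2 still conflicts with its list.

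Several stronger readings are tempting and are not supported:
- *Primary data are lost selectively.* This is conditional. If the closing sentence governs, patients with AEs remain in the trial and 7.1 asks for their Week 24 study. Exits after Week 24 cost no primary data.
- *The pregnancy texts contradict each other on stopping drug versus leaving.* They do not. Leaving the trial includes stopping the drug, and neither 7.1 nor Appendix 4 says that the patient stays.
- *Sites will differ.* The trial is single-center, so any inconsistency would be between patients.
- *The disposition tables cannot be consistent, or new eCRF items are needed.* The tables in SAP 4.2.1 report treatment completion, reasons, durations and last visit; none uses the 7.2 definition. SAP Appendix B already draws on separate treatment and trial completion forms.

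It is also fair that patients who stop drug but stay are already covered by the follow-up text in 7.1. The gap is confined to patients handled under 7.2, and to the SAP sentence.

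**Conclusion.** The point holds as an internal contradiction with a limited, conditional consequence. Protocol 7.2 gives two answers on who is withdrawn, its exit route omits the only visit that yields the primary and key secondary values after baseline, and SAP 4.3.1 sits against its own estimand strategy.

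The size cannot be known because no dropout rate is stated. With one of 10 lost, the primary mean would be overstated by 0 to 72 g/day. This assumes that the nine observed patients average the phase 2 value and that the lost patient's change lies between 719 and 0. A change outside that range would move the bias beyond these limits. A reader might infer that the primary conclusion is at risk; in this scenario it is not, and primary power stays at 98.2% even with 6 values. What is exposed is the size of the reported effect, and key secondary power if the effect size is near 1.15.

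**What to change.** 1. Reconcile Protocol 7.1, 7.2, 8.4.5 and Appendix 4 with SAP 2.1.1.1 and 4.3.1, so that each trigger leads to one stated status: off treatment but in the trial, or withdrawn from the trial. Make the closing sentence of 7.2 agree with its list. Which status applies to each trigger is for the sponsor to decide.
2. In the paragraph of 7.2 marked as important, extend the request already made in 7.1. A patient covered by 7.2 before Week 24, who has not withdrawn consent or refused contact, is asked to attend the planned Visit 9 balance study if the Investigator judges it safe, in addition to Weeks 52 and 56.
3. Amend the SAP 4.3.1 sentence on data collection so that Week 24 data obtained after treatment has stopped are collected and included under the treatment policy strategy.

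The cost is amendment wording in two documents. Visit 9 is already planned for every patient, so the burden is one in-house stay for a patient who is off drug and agrees to attend. For a patient who left because participation itself was judged unsafe, the safety condition means that no such stay is requested.
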